### I. Background and Significance:

Major depression is both common and burdensome, affecting over 15 million Americans in 2010 and costing over 210 billion dollars. Moreover, existing treatments for depression often do not achieve remission. Only a third of patients will achieve remission with their first antidepressant trial, and up to a third will not achieve remission even after multiple medication trials. Patients who do not respond to at least one antidepressant trial can be deemed treatment-resistant (although treatment-resistance exists along a continuum). It is possible that treatment resistant depression (TRD) may require novel treatment approaches. Many of the most frequently used pharmacologic treatments for depression target the monoamine systems or are hypothesized to exert an effect by affecting monoamine function, and other drugs under evaluation are generally focused on other neurotransmitter systems. A focus on other systems may yield additional treatment options for treatment-resistant depression.

Increasingly, converging lines of evidence support a role for inflammation in the pathogenesis of depression. Elevations in the inflammatory markers C-reactive protein (CRP) and interleukin-6 (IL-6) are found in patients with depression as compared to normal controls. Elevated levels of CRP can also predict the onset of depression, suggesting a role for inflammation in its pathogenesis. Tumor necrosis factor  $\alpha$  (TNF- $\alpha$ ), too, has been demonstrated to be elevated in major depression. When healthy volunteers are given endotoxin infusions, which stimulate the release of cytokines, the cytokine levels were associated with the development of mood disorder symptoms. Administration of exogenous cytokines including TNF- $\alpha$  and interferon- $\alpha$  (IFN-  $\alpha$ ) have produced classical symptoms of depression in previously mood-stable individuals. Finally, antidepressant treatment has been demonstrated to reduce levels of IL-6 and CRP in depressed patients, and a lack of response to treatment has been associated with persistent elevations in these inflammatory markers. Taken together, the above suggests a role for inflammation in the development of depression and given this, investigation of anti-inflammatory agents in the treatment of depression is indicated.

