## **III. Subject Selection:**

This study is a randomized, double-blind, placebo-control trial. The trial will enroll 74 adult subjects with treatment-refractory major depressive disorder, 37 per group. Assuming a non-completion rate of approximately 20%, as is customary in clinical trials of antidepressants, we will enroll a total of 74 subjects, anticipating 60 study completers. Subjects will all be recruited through outpatient psychiatric clinics affiliated with Brigham and Women's Hospital, through physician referral, print advertisements, and flyers.

Inclusion criteria:

- Aged 18-55
- Current diagnosis of major depressive disorder
- Hamilton Depression Rating Scale score of  $\geq 21$

- Stable treatment regimen (no medication changes or changes in psychotherapy treatment in past 8 weeks, and no participation in stepped treatments, such as completion of a course of cognitive behavioral therapy, during the trial)
- Failed to remit with up to 2 sequential antidepressant trials, or combination of 1 antidepressant and 1 augmentation agent
- Women of childbearing age must agree to use an approved method of contraception for the duration of the study

Exclusion criteria:

- Active suicidal ideation
- History of manic episodes or psychosis
- Alcohol or substance use disorder within the past 6 months
- Comorbid neurologic condition affecting the central nervous system
- Comorbid autoimmune condition
- History of thyroid disease or a current abnormal TSH
- Active or recent (within the past month) infection (such as otitis, pneumonia, urinary tract infection); temperature  $> 100.3$  or WBC count  $> 11$  K/microL will be considered evidence of active infection even in the absence of other symptoms
- History of GI bleed
- History of stroke
- History of a bleeding disorder
- Platelet count  $< 150,000/\text{mm}^3$  on initial screening
- On a blood-thinning agent or taking NSAIDs daily
- Current use of oral steroids or other immunomodulating medications
- Salicylate sensitivity
- Pregnancy or breastfeeding
- GFR less than  $60 \text{ mL/min}/1.73\text{m}^2$
- Current use of another nephrotoxic medication

The decision not to restrict participation to subjects utilizing a single medication was made to better reflect clinical practice, in which a variety of SSRI (selective serotonin reuptake inhibitors) and SNRI (serotonin-norepinephrine reuptake inhibitors) are used as first-line agents, and in order to enhance the generalizability of study findings.

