### Study Visit 1 (screening and study week 0):

At the first study visit, the principal investigator or co-investigator study physician will obtain informed consent. Details about the study, including objectives, procedures, and potential risks and discomforts will be discussed with the subject by a physician investigator. Subjects will be given the opportunity to ask any questions and will be given ample time to consider whether they wish to participate. They will be informed that refusal to participate will not interfere with their subsequent medical care.

The clinical study staff will then administer the Hamilton Depression Rating Scale (HDRS) and the Mini International Neuropsychiatric Interview (MINI) to confirm the subject has an active diagnosis of major depressive disorder (as defined by DSM V criteria) and rule out diagnoses of exclusion (namely mania, psychosis or hypomania). Subjects with active suicidal ideation, represented by a score of  $>2$  on HDRS item 3, will be ineligible for the study and will be referred for urgent or emergent clinical assessment as indicated in the safety plan. Subjects will complete the Quick Inventory of Depression Symptomatology-Self Report (QIDS-SR), the MGH Antidepressant Treatment Response Questionnaire, the Systematic Assessment for Treatment Emergent Events (SAFTEE), and the Childhood Experience of Care and Abuse Questionnaire (CECA-Q3). The QIDS-SR and SAFTEE are customary for antidepressant medication clinical trials. The CECA documents early life stressors that can both increase risk for depression and impact cytokine levels through the lifespan.

All subjects will have a complete blood count drawn to measure their white blood cell and platelet counts and a thyroid screening hormone test. Subjects will also have labs drawn to measure blood urea nitrogen, creatinine, and electrolytes. Subjects will be asked about co-morbid neurologic, rheumatologic, and bleeding disorders and recent history of infection. Subjects will be asked to report on their use of oral steroid medications, non-steroidal anti-inflammatory drugs (including aspirin, ibuprofen, naproxen, meloxicam, celecoxib, diclofenac, nabumetone, ketoprofen, and indomethacin), warfarin, heparin, and other anticoagulants (including clopidogrel, enoxaparin, rivaroxaban, apixaban, edoxaban, dabigatran, and fondaparinux).

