## **VI. Biostatistical Analyses:**

The baseline data to be collected and analyzed include: subject age at enrollment, gender, age of depression onset, number of previous depressive episodes, HDRS. HDRS will be repeated at the subsequent study visits for analysis. Cytokine levels will also be analyzed at the initial and final visits. The planned study end-point is at eight weeks after initiation, and is not based on any pre-determined treatment response. Exploratory analysis of the immunologic profiling data will be performed as well, with a goal to detect within-subject changes over the course of the study and to discern any differences between non-responders and responders.

Baseline measurements for continuous variables (e.g., age of onset, current age) will be assessed by t-test. Categorical measurements, such as gender, will be compared with Fisher's exact test or chi-square as appropriate. For the primary study outcome, the change in HDRS in the treatment versus control groups will be evaluated with analysis of covariance (ANCOVA), with initial HDRS score as a covariate.

Power calculations were based on a prior open-label trial of salicylic acid as an augmentation agent to fluoxetine, which found an average 15-point drop in HDRS score over a 4-week trial. To be conservative, we are assuming a much smaller effect size, and so this study is powered to detect a 3-point difference in HDRS score, a difference which is deemed to be clinically significant. 29 participants per group are required to detect this clinically significant difference assuming .80 power and a two-sided alpha of 0.05. Assuming a non-completion rate of approximately 20%, customary in clinical trials of antidepressants, we will enroll 74 subjects, anticipating 60 completers.

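### The primary ANCOVA leaves out the number of failed treatment steps, a baseline variable already obtainable at Visit 1; if it is prognostic, some precision is lost

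*Combined protocol and SAP*

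**What the plan says.** - **Entry (section III, inclusion criteria).** Subjects qualify if they have "Failed to remit with up to 2 sequential antidepressant trials, or combination of 1 antidepressant and 1 augmentation agent". One-step and two-step histories are therefore both admitted.
- **Background (section I).** Failure of one antidepressant trial is enough to be called treatment-resistant, "although treatment-resistance exists along a continuum".
- **Visit 1 (section V).** Subjects complete "the MGH Antidepressant Treatment Response Questionnaire, the Systematic Assessment for Treatment Emergent Events (SAFTEE" and other instruments, and report their current depression treatments, before pill packets are handed out. The documents do not say how the MGH questionnaire is scored or used.
- **Baseline data for analysis (section VI).** The list is "subject age at enrollment, gender, age of depression onset, number of previous depressive episodes, HDRS". Neither failed steps nor the MGH questionnaire is on it.
- **Primary model (section VI).** The change in HDRS "will be evaluated with analysis of covariance (ANCOVA), with initial HDRS score as a covariate". No other covariate is named, and no randomisation stratum is described.
- **Target (section VI).** According to the plan, "this study is powered to detect a 3-point difference in HDRS score", with 29 per group, 80% power and two-sided alpha 0.05.

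**The concern.** The trial population is defined by failed treatment, and the admitted subjects differ in how much of it they have had. Someone must count the failed steps in order to apply the entry criterion, so the information exists before treatment starts. A baseline variable that predicts the outcome in both arms reduces the residual variance when it enters the ANCOVA. If it is left out, that variance stays in the error term.

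What is at stake is the precision of the aspirin-placebo difference in a trial of about 60 completers. Timing matters too: a covariate named before unblinding is uncontroversial, whereas one added afterwards can be challenged as data-driven.

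**Working it through.** **1. The plan's own figure.** Section VI gives no SD, so 29 per group can only be solved backwards.
- Normal approximation: SD = 3 × √(29/2) / (1.960 + 0.842) = 4.08.
- t-test: SD = 4.01. With SD 4.0 and 29 per group, t-test power is 0.801.
- Dropout: 29 / 0.80 = 36.25, rounded up to 37 per group, or 74 in total, as stated. 74 × 0.80 = 59.2 completers, against the 60 stated, which is close enough.

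**2. Inputs for the check.** From the plan: the 3-point target, two-sided alpha 0.05, and about 59 completers (29.5 per arm). Assumed, because the documents give none of these: residual SD 4.0 after baseline HDRS (near the implied value); share p of subjects with two failures, 0.3 to 0.5; and d = 1 to 3 points less improvement in those subjects.

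**3. Formulas.** Share of residual variance explained: R² = p(1−p)d² / 16. SD after adjustment: 4√(1−R²). Noncentrality: 3 / (SD × √(2/29.5)), where √(2/29.5) = 0.2604. Power comes from the noncentral t. Error degrees of freedom are 59 − 3 = 56 without the covariate and 55 with it.

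| p | d | p(1−p)d² | R² | SD after | Power |
|---|---|---|---|---|---|
| not in model | – | – | – | 4.00 | 0.808 |
| any | 0 (useless covariate) | 0 | 0 | 4.00 | 0.808 |
| 0.3 | 1 | 0.21 | 0.013 | 3.97 | 0.813 |
| 0.5 | 1 | 0.25 | 0.016 | 3.97 | 0.814 |
| 0.3 | 3 | 1.89 | 0.118 | 3.76 | 0.854 |
| 0.5 | 3 | 2.25 | 0.141 | 3.71 | 0.863 |

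**4. Sensitivity to the SD** (normal approximation, 29 per group, p = 0.5, d = 1 to 3). At the implied SD of 4.08, power goes from 0.800 to 0.806-0.854. At an assumed SD of 7, it goes from 0.371 to only 0.373-0.386.

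**5. Is chance imbalance a separate harm?** Take the strongest case, p = 0.5 and d = 3. Imbalance between arms moves the unadjusted estimate with SD 3 × √(2 × 0.25 / 29.5) = 0.39 points. The standard error is 4.00 × 0.2604 = 1.042 without the covariate and 3.708 × 0.2604 = 0.966 with it. Since 0.966² + 0.39² ≈ 1.085 ≈ 1.042², the imbalance is already contained in the unadjusted standard error. It is the same cost as the lost precision, not an additional one.

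**The case against.** The best defence is that a sparse model with the baseline outcome as its only covariate is valid and reasonable at this sample size. Age of onset, number of episodes, BMI and childhood adversity are also collected, and the documents do not rank any of them as predictors. The questionnaire may be there only to verify eligibility, and a 1-versus-2 variable is defined nowhere. The split, the prognostic difference and the SD are all assumptions. The unstated SD matters far more: at 29 per group, power (normal approximation) is 0.627 if the SD is 5.

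Much of this stands, and it keeps the point small. It does not remove it. The failed-step count is the one candidate that also defines the trial population, and a verification use does not prevent its use as a covariate. The missing SD is a separate matter.

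A reader might infer three stronger things that the documents do not support:
- *That the background says remission falls with each failed trial.* Section I says a third remit on the first antidepressant and up to a third have not remitted after several. On those figures, two thirds fail the first step and at least half of them remit later. No rate per step is given, and the continuum remark concerns definition, not prognosis.
- *That the primary result is biased, or that chance imbalance goes uncorrected.* Randomisation keeps the ANCOVA valid, and step 5 of the working shows that the standard error already covers such imbalance.
- *That the biomarker models need the same term.* Baseline cytokine level is not randomised, and section I links non-response to persistently raised markers, so the idea is reasonable. However, nothing shows that failed-step count confounds those models. They do not list even baseline HDRS, which has the stronger claim to inclusion.

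**Conclusion.** The point holds as a modest matter of efficiency. Entry mixes failure histories, the information is available before treatment, and section VI uses it nowhere. Whether the count predicts HDRS change is plausible but not shown.

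Under the stated assumptions, prespecifying it lifts power for 3 points from about 81% to between 81% (1-point prognostic difference) and 86% (3 points, even split). The gain shrinks to 1.5 percentage points or less if the SD is 7. If the covariate explains nothing, power stays at 0.808. There is no bias and no type I error inflation in the randomised comparison. The change is worth making because it costs almost nothing, not because the present analysis is invalid.

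**What to change.** Before unblinding, state in section VI that the primary model is HDRS change on treatment, baseline HDRS and number of failed treatment steps. Code the count as 1 versus 2, with one antidepressant plus one augmentation agent counted as 2, and take it from the Visit 1 treatment history. Add the variable to the baseline data listed in the same section. If the sponsor prefers the present model, one sentence giving the reason would do.

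Adding the term to the biomarker models of HDRS change is optional and secondary.

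Cost: a sentence or two of SAP wording, a coding rule, and one error degree of freedom (56 to 55). No new subjects, visits or measurements are needed.

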Subjects will be asked to report on their age at first depression diagnosis, and number of depressive episodes, as well as existing treatments for depression, including names and dosages of medications, type(s) of psychotherapy, frequency of meetings with a psychiatrist, psychologist, social worker, or other counselor, and any other treatment modalities they engage in. Female subjects will also be asked to report whether they have regular monthly menstrual cycles, the date of their last menstrual period, and whether they are taking hormonal contraceptives or not. Women of child-bearing age will also receive a qualitative urine HCG pregnancy test. Female subjects will have blood drawn for follicle-stimulating hormone (FSH), estradiol, and progesterone levels. All subjects' temperature will be taken to assess for infection. If their temperature is greater than 100.3F, they will be excluded from the study. Subjects determined to be ineligible based on the results of the screening or screening labs will be thanked for their participation and conclude their participation.

Ten mL of subjects' blood will be separated by centrifuge and the serum analyzed for an array of 60 cytokines and chemokines including C-reactive protein (CRP), interleukin-6 (IL-6), and tumor necrosis factor alpha (TNF-alpha); assays will be performed using a Luminex bead-based immunoassay. Serum will be stored into small aliquots at -80°C to avoid repeated freeze-thaw cycles. 25 µl of serum per subject will be used for Luminex studies as previously reported. Expression data will be analyzed by Luminex software. All samples will be drawn between 8:00 AM and 10:00AM in order to minimize the effect of circadian fluctuations in cytokine levels. Subject's height and weight will be taken to allow for calculation of BMI; prior work has demonstrated a U-shaped relationship between BMI and pro-inflammatory cytokines, with higher values associated with underweight and obesity.

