To evaluate gene profiles of peripheral immune cells, peripheral blood mononuclear cells (PBMCs) will be prepared by Ficoll-Paque PLUS gradient centrifugation from the blood in order to isolate T cells and monocytes. Frequency of CD4+, CD8+, and CD14+ cells will be measured. PBMCs will be stored into aliquots at -80°C. For transcriptomic analysis, Fluidigm Biomark technology will utilize microfluidic technology to perform high throughput gene expression measurements with real time PCR. RNA will be processed from flow cytometry-sorted activated/memory CD4+ (CD3+CD44hi), and CD8+ (CD3+CD44hi) T cells, as well as CD14+ monocytes. A panel of 96 T cell or monocyte-specific genes for pro-inflammatory, anti-inflammatory, chemokine, chemokine receptor, and signaling molecules will be measured.

To allow for the eventual, detailed characterization of the subjects' immunologic profiles, whole blood samples will also be banked for subsequent processing at the [name] Lab at Brigham and Women's Hospital/Harvard Medical School. The samples will be assayed for antigens using the following technique: over 500 individual antigens (proteins, lipids, myelin peptides) are spotted on slides by a robot, after which the slides are incubated with serum from subjects with depression and an immune signature is developed. The samples will also be assayed for microRNAs, non-coding RNAs that modulate immune function.

Subjects who meet inclusion criteria for the study will be given their pill packets for the ensuing 8 weeks, consisting of blister packs for a daily dose of aspirin 325mg in those randomized to the treatment condition and of blister packs of a placebo pill of the same size, shape, and color as the aspirin tablet in those randomized to the control condition. Subjects will be instructed to take

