their pills in the evening before bed; in cardiovascular studies aspirin has had greater efficacy and better tolerability when taken at this time of day. Subjects will be instructed not to take aspirin over the counter during the study, and to inform study staff of their use of other over-the-counter anti-inflammatory medications. All subjects will be instructed to also continue their existing antidepressant treatment regimen but not to engage in new treatments or therapies during the course of the study. If new treatments are deemed clinically necessary during the course of the study subjects are instructed to contact study staff immediately to inform them of the change.

Study Visit 2 and 3 (weeks 2 and 4):

At study visits 2 and 3, subjects will be asked about their compliance with the study drug and about any adverse effects; they also will again complete the SAFTEE. They will be asked about any changes to their medications or psychiatric treatment. Study staff will re-administer the Hamilton Depression Rating Scale (HDRS) and subjects will again complete the QIDS-SR. Blood will be drawn for repeat cytokine/chemokine immunoassay, BUN, creatinine, and electrolytes measurements. If preferred, the subject can complete the psychometric measures by telephone and online portal and omit the blood draws at these visits.

Study Visit 4 (week 8):

At study visit 4, study staff will re-administer the Hamilton Depression Rating Scale (HDRS) and blood will again be drawn for repeat cytokine/chemokine immunoassay, including measures of CRP, IL-6, BUN, creatinine, electrolytes and TNF-alpha. Subjects will again complete the QIDS-SR and the SAFTEE, and will be asked about any changes to their medications or psychiatric treatment and any changes in their health status. Platelet count and FSH, estradiol, and progesterone levels as appropriate, will also be repeated. Follow up samples for the detailed immunologic profiling will also be drawn. Serum salicylate concentrations will be drawn (to confirm compliance with study medication in those subjects assigned to the aspirin condition, and to confirm subjects not assigned to the aspirin condition were not using it).

Subjects will be advised to follow up with their current outpatient psychiatric providers within two weeks of ending participation in the study.

Remuneration:

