Subjects who complete the study including 4 in-person visits will receive a total of \$200 (\$45 for the first study visit, \$40 each for the second and third study visits (\$20 if no blood draw and subject completes questionnaires remotely), and \$75 for the last study visit) in four payments sent by mail after each visit. All participants will receive complementary parking for study visits.

Data storage:

At each study visit, the study staff will enter the data into case report forms in paper binders, as well as in our institution's research electronic data capture platform (REDCap). All laboratory values will be reviewed by a physician investigator. Paper files matching the case report forms in REDCap, and including the consent form, screening materials, and any additional correspondence will be stored in a locked filing cabinet in the office of the study staff at Brigham and Women's Hospital. All electronic study data will be stored securely on REDCap and de-identified prior to data analysis. Only group data will be reported.

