## **IX. Monitoring and Quality Assurance:**

The principal investigator, [name], will be responsible for monitoring the safety of all subjects. In the event that [name] is unavailable, physician co-investigators will be available to monitor the safety of all subjects.

All study staff are primarily located at Brigham and Women's Hospital. Study safety meetings, including the principal investigator, study coordinators, and study physicians will occur regularly to review the progress of currently-enrolled subjects and any reported side effects.

The Principal Investigator will assess all patients with regard to stopping criteria. In general terms, a subject will be discontinued from the study for the following reasons:

- 1) The subject has experienced an adverse event that, in the opinion of the principal investigator requires early termination
- 2) The subject's thoughts or behaviors become a safety risk at any time during the trial
- 3) The subject experiences a 20% drop in GFR during the course of the study
- 4) The subject withdraws consent

Specific to this study, subjects will be monitored for suicidal thoughts at both visits and for adverse events as well. Subjects who develop active suicidal ideation, represented by a score of  $>2$  on HDRS item 3, will be referred for urgent or emergent clinical assessment. A patient who develops active suicidal thoughts will be urgently evaluated by a study physician. In any case where there are acute safety concerns arising from suicidality (such as a plan or actual intent), the patient will be sent to the BWH Emergency Department for further evaluation under Section 12a, and in compliance with hospital policies. If there are no acute safety concerns based on the urgent evaluation, the patient will be monitored according to study protocol and instructed to contact study staff immediately with any worsening in their mood or thinking. The study physician will review the urgent or emergent safety assessment and determine if the subject can continue in the study. Any subject who requires a level of care exceeding customary outpatient services (i.e., psychiatric hospitalization or participation in a partial hospital program) will be removed from the study. If a subject must be transferred from the study into clinical care, the study physicians will continue to follow the subjects until they are accepted into appropriate, longer-term care, if clinically indicated.

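### A subject who omits both interim blood draws has no scheduled creatinine between baseline and week 8, so no scheduled measurement lets the 20% GFR criterion stop dosing early

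*Combined protocol and SAP*

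**What the plan says.** The third discontinuation reason in Section IX reads: "The subject experiences a 20% drop in GFR during the course of the study". Section V schedules renal chemistry at every visit. It is among the screening labs at Visit 1. At Visits 2 and 3, "Blood will be drawn for repeat cytokine/chemokine immunoassay, BUN, creatinine, and electrolytes measurements". At Visit 4 the repeat panel is described as "including measures of CRP, IL-6, BUN, creatinine, electrolytes and TNF-alpha".

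The text for Visits 2 and 3 then gives the subject a choice: "If preferred, the subject can complete the psychometric measures by telephone and online portal and omit the blood draws at these visits". The Remuneration paragraph prices that choice, paying $20 instead of $40 for each of these visits "if no blood draw and subject completes questionnaires remotely". No make-up draw, local laboratory test or minimum of one interim draw is described.

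On drug supply, Visit 1 states that eligible subjects "will be given their pill packets for the ensuing 8 weeks". The dose is one 325 mg aspirin tablet or matching placebo daily, taken in the evening.

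**The concern.** Of the four listed discontinuation reasons, the GFR criterion is the only one that needs a laboratory value. The opt-out is worded for all blood draws at the two interim visits, so it removes the safety chemistry along with the research sample. Because the whole supply is dispensed at the start, no resupply step would prompt a check either.

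What is at stake is the chance to stop drug in time. A subject can follow the protocol exactly and finish the course before anyone has a scheduled value to compare with baseline. The criterion covers falls that matter by the trial's own standard: entry requires a GFR of at least 60, and a 20% fall from 60 gives 60 × 0.80 = 48. Any baseline below 75 would end under the entry limit, since 75 × 0.80 = 60.

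**Working it through.** The plan states no figure to reproduce. The check is a reading of the schedule under each attendance pattern that Section V permits.

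Inputs:
- Creatinine at weeks 0, 2, 4 and 8 (Section V, Visits 1 to 4).
- The draw may be omitted at week 2, week 4 or both (Section V, Visits 2 and 3, and Remuneration).
- One dose daily for 8 weeks, so 8 × 7 = 56 doses, all dispensed at Visit 1 (Section V, Visit 1).
- Assumption: dosing starts on the evening of Visit 1, visits fall on their nominal days and no dose is missed.

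Formulas:
- Longest gap in days = 7 × the largest difference in weeks between consecutive scheduled values.
- Doses left at the first post-baseline value = 56 − 7 × the week of that value.

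| Interim draws taken | Creatinine at weeks | Interim values | Longest gap | Doses left at first post-baseline value |
|---|---|---|---|---|
| Both | 0, 2, 4, 8 | 2 | 7 × 4 = 28 days | 56 − 14 = 42 |
| Week 2 only | 0, 2, 8 | 1 | 7 × 6 = 42 days | 56 − 14 = 42 |
| Week 4 only | 0, 4, 8 | 1 | 7 × 4 = 28 days | 56 − 28 = 28 |
| Neither | 0, 8 | 0 | 7 × 8 = 56 days | 56 − 56 = 0 |

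Only the last row leaves the criterion without a scheduled value while drug remains. Doses are counted at the draw; the time taken to report a result would reduce them slightly in every row.

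The same table shows what one required draw would do. A subject in the last row who has the draw moves to the second or third row: 1 interim value, with 42 or 28 doses left. A gap of 42 days (after week 2) or 28 days (after week 4) then remains before the final value. A subject who still has no draw and is allowed to continue stays in the last row.

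The documents give neither the share of subjects who would omit both draws nor a renal event rate. The number affected can therefore only be bounded, at 0 to 74, and missed GFR falls cannot be estimated.

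**The case against.** The strongest reply is that the criterion is not tied to scheduled draws and that other safeguards continue. Nothing bars an unscheduled creatinine. Adverse effects, the SAFTEE and medication changes are covered at weeks 2 and 4. Subjects may not take over-the-counter aspirin and must report other over-the-counter anti-inflammatory drugs. Section IX has the principal investigator assess every subject against the stopping criteria, with regular safety meetings, and an adverse event can end participation on its own.

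The population is also at low risk: aged 18 to 55, GFR of at least 60, with daily NSAID use and other nephrotoxic drugs excluded, on 325 mg daily for 8 weeks. Remote visits are a reasonable concession to retention.

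All of this stands, and it makes the point modest. It does not close the gap. None of these safeguards yields a GFR unless someone orders a test, and the protocol names no trigger for one when draws are omitted. Physician review of laboratory values can cover only values that exist.

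A reader might infer that the criterion cannot work at all for these subjects, or that a fall would go undetected. The documents support neither reading. An unscheduled test could still trigger the criterion, and the week 8 value still shows a fall. What is lost is early stopping through the planned schedule.

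**Conclusion.** The concern holds, limited to subjects who omit both interim draws and to scheduled measurements. For them there are 0 scheduled creatinine values between baseline and week 8, a 56-day gap, and 0 of 56 doses left when the first post-baseline value is taken. The schedule reading is certain from the text; the dose count rests on the nominal visit and dosing days.

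This is a minor point, and the remedy is a cheap improvement. A reader might take it as evidence of material renal risk, but the documents give no event rate or opt-out rate that would support that. The sample size and the primary HDRS comparison are unaffected.

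**What to change.** Keep the remote questionnaires and the optional cytokine sample, and take the renal chemistry out of the opt-out. In Section V, Visits 2 and 3, add to the opt-out sentence an exception such as: *This option does not remove the renal check. Each subject taking study drug will have BUN, creatinine and electrolytes measured once, at week 2 (preferred) or week 4. A chemistry-only draw may be taken at any time of day. If none has been obtained by the week 4 visit, a study physician decides whether study drug continues and records the reason.*

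Two features of the plan make this easy. Section VI analyzes cytokines at the initial and final visits, so the interim cytokine sample can stay optional. The morning window is justified by cytokines alone ("All samples will be drawn between 8:00 AM and 10:00AM in order to minimize the effect of circadian fluctuations in cytokine levels"), so a chemistry-only draw need not keep it. The Remuneration paragraph should state the payment for remote questionnaires with a draw, a combination it does not now cover.

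The gain depends on the draw being done. For a subject allowed to continue without one, the only gain is a documented physician decision at week 4.

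The cost is a short amendment and no new test: of the 74 × 2 = 148 interim chemistry draws already planned, at most 74 become required. If the $40 rate applies, the added payment is at most $40 − $20 = $20 per subject, or 74 × $20 = $1,480 if all would otherwise have omitted both. Phlebotomy, parking and the extra attendance come on top.

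The main downside is a required draw for subjects who prefer fully remote visits, with a possible small loss of retention. The margin there is thin. Section VI says "29 participants per group are required to detect this clinically significant difference", so 2 × 29 = 58 completers are needed, against 74 × 0.80 = 59.2 expected (the plan says 60), a margin of 1.2 to 2. The any-time draw, and a physician decision in place of automatic removal, limit that cost. Requiring both draws would cut the longest gap to 28 days but end the draw-free remote visit, and is not proposed.
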